# 7.6.3.2 Protocol-Specific Recommendation for Management of Hepatic Events in HCC Participants

The algorithms recommended for the management of irAEs in this protocol are in Appendix 6. Protocol-specific recommendation for the management of hepatic events in HCC participants are as follows:

- Dose delay criteria for hepatic events are outlined in Section 7.6.3.1. If AST or ALT levels do not improve with a dose delay of 3 to 5 days, or if the levels worsen, steroid therapy should be initiated at 0.5 mg/kg/day to 2 mg/kg/day methylprednisolone or oral equivalent
- For ALT or AST levels > 8× ULN, steroid therapy should be initiated promptly at 1 mg/kg/day to 2 mg/kg/day methylprednisolone IV, intramuscularly, or oral equivalent
- For all participants receiving steroid treatment for hepatic events, the BMS Medical Monitor should be consulted within 24 hours after initiation of steroids. Gastroenterology consult is recommended
- If AST or ALT levels do not improve within 3 to 5 days after the start of steroid therapy, or the levels worsen after the start of steroid therapy, discussion with the BMS Medical Monitor regarding the possibility of adding mycophenolate mofetil 1 g twice daily should occur
- Tapering of steroids can start once AST or ALT levels have declined by 1 CTCAE grade. Steroids should be tapered slowly, over no less than 1 month
- As outlined in Section 7.6.4, study therapy may resume when AST or ALT have returned to Grade 1 or baseline unless the AE meets the criteria for permanent discontinuation (Section 8.2). The BMS Medical Monitor must be consulted prior to resuming study treatment for all participants who required steroid intervention.

#### 7.6.4 Criteria to Resume Treatment

Participants may resume treatment with study drug if they have completed AE management (ie, corticosteroid taper) or are on  $\leq 10$  mg daily prednisone or equivalent and meet the requirements per described below.

Prior to re-initiating treatment in a participant with a dosing delay lasting > 8 weeks, the Medical Monitor (or designee) must be consulted. Continue tumor assessments per protocol even if dosing is delayed. Continue periodic study visits to assess safety and laboratory studies weekly or more frequently if clinically indicated during such dosing delays.

When criteria to resume treatment for nivolumab, ipilimumab, and BMS-986253 (or placebo) are met, resume all study drugs unless the investigator determines that one of the agents must be discontinued due to toxicity attributed to that agent alone.

Subsequent dosing with study therapy may resume once drug-related non-DLT AEs resolve to Grade 1 or baseline for the drugs being resumed.

Participants experiencing AEs not meeting criteria for permanent discontinuation for the drugs being resumed as outlined in Section 8.1 may resume treatment with study medication under the following criteria:

- Participants may resume treatment with study treatment when the drug-related AE(s) resolve to Grade ≤ 1 or baseline value, with the following exceptions:
  - Participants may resume treatment in the presence of Grade 2 fatigue.
  - Participants who have not experienced a Grade 3 drug-related skin AE may resume treatment in the presence of Grade 2 skin toxicity.
  - Participants with Grade 2 uveitis, episcleritis, iritis, eye pain, or blurred vision not meeting DLT criteria (Section 7.6.1) must resolve to baseline prior to resuming study therapy.
- For participants with Grade 2 AST, ALT, or total bilirubin elevations, dosing may resume when laboratory values return to baseline and management with corticosteroids (if needed) is complete.
- Participants with combined Grade 2 AST/ALT and total bilirubin values meeting DLT criteria (Section 7.6.1) should have treatment permanently discontinued.

#### • Criteria for HCC Participants:

- Participants with baseline Grade 1 AST, ALT, or total bilirubin who require dose delays, for reasons other than a drug-related hepatic event, may resume treatment in the presence of Grade 2 AST, ALT, or total bilirubin increases.
- Participants who require dose delays for drug-related increased AST, ALT, or bilirubin may resume treatment when hepatic parameters are at baseline or Grade 1, and after discussion with the BMS Medical Monitor
- Participants with AST, ALT or bilirubin values meeting permanent discontinuation parameters (Section 7.6.1) should have treatment permanently discontinued.

• Drug-related pulmonary toxicity, diarrhea, or colitis, must have resolved to baseline before treatment is resumed. Participants with persistent Grade 1 pneumonitis after completion of a steroid taper over at least 1 month, may be eligible for re-treatment if discussed with, and approved by, the BMS Medical Monitor.

- Participants with drug-related endocrinopathies adequately controlled with only physiologic hormone replacement may resume treatment.
- Participants with confirmed SARS-CoV-2 infection may resume treatment after 1) at least 10 days (20 days for severe/critical illness) have passed since symptoms first appeared, positive RT-PCR test result, or positive viral antigen test result, 2) resolution of acute symptoms (including at least 24 hours has passed since last fever without fever reducing medications), 3) evaluation by the investigator with confirmation that there are no sequelae that would place the participant at a higher risk of receiving investigational treatment, and 4) consultation by the Medical Monitor. For suspected cases, treatment may also resume if SARS-CoV-2 infection is ruled-out and other criteria to resume treatment are met.
  - Prior to re-initiating on-study treatment in a participant with a dosing delay lasting
     ≥ 8 weeks due to SARS-CoV-2 infection, the Medical Monitor/designee must be
     consulted.

## 7.6.5 Exceptions to Permanent Discontinuation Criteria

Any drug-related AE occurring at any time that meets DLT criteria as outlined in Section 7.6.1 will require permanent discontinuation of all study drugs, unless the investigator determines that one of the agents must be discontinued due to toxicity attributed to that agent alone.

Permanent discontinuation is not required for the following:

- Grade 3 diarrhea, nausea, vomiting, or abdominal pain that returns to Grade 1 or baseline within 3 days with medical intervention.
- Grade 3 pruritus or rash that returns to Grade 1 or baseline within 7 days with medical intervention.
- Isolated Grade 3 or 4 electrolyte imbalances/abnormalities that are not associated with clinical sequelae and are corrected with supplementation/appropriate management within 3 days of their onset.
- Grade 4 neutropenia < 7 days in duration.
- Grade 4 lymphopenia or leukopenia.
- Grade 3 or 4 increase in amylase or lipase that is not associated with clinical or radiographic evidence of pancreatitis.
- Grade 3 infusion reaction that return to Grade 1 in < 6 hours.
- Grade 3 CRS that returns to Grade 1 in < 6 hours.
- Grade 3 fever not associated with hemodynamic compromise (eg, hypotension, clinical, or laboratory evidence of impaired end-organ perfusion).
- Grade 3 tumor flare (defined as pain, irritation, or rash that localizes to sites of known or suspected tumor).

- Grade 3 fatigue.
- Grade 3 or 4 drug-related endocrinopathy AEs, such as adrenal insufficiency, adrenocorticotropic hormone, hyper- or hypothyroidism, or glucose intolerance, which resolve or adequately controlled with physiologic hormone replacement (corticosteroids, thyroid hormones) or glucose-controlling agents, respectively, may not require discontinuation after discussion with and approval from the BMS Medical Monitor.

All participants who discontinue IP should comply with protocol specified follow-up procedures as outlined in Section 8.1. The only exception to this requirement is when a participant withdraws consent for all study procedures including post treatment study follow-up or loses the ability to consent freely (eg, imprisonment, involuntarily incarceration for the treatment of either a psychiatric or physical illness).

If study treatment is discontinued prior to the participant's completion of the study, the reason for the discontinuation must be documented in the participant's medical records and entered on the appropriate case report form (CRF) page.

## 7.6.6 Management of Drug-related Infusion Reactions

Since BMS-986253, nivolumab, and ipilimumab contain only human Ig protein sequences, they are unlikely to induce hypersensitivity reactions. However, infusion reactions due to T-cell activation and cytokine release may occur in combination of both agents. If such a reaction were to occur, it might manifest with fever, chills, rigors, headache, rash, pruritus, arthralgia, hypotension, hypertension, bronchospasm, or other allergic-like reactions. All Grade 3 or 4 infusion reactions should be reported within 24 hours to the BMS Medical Monitor and reported as an SAE. Infusion reactions should be graded according to NCI CTCAE v4.03 guidelines.

Treatment recommendations for infusion reactions are provided below and may be modified based on local treatment standards and guidelines, as appropriate.

For Grade 1 symptoms (mild reaction; infusion interruption not indicated; intervention not indicated):

• Remain at bedside and monitor participant until recovery from symptoms. The following prophylactic pre-medications are recommended for future infusions: diphenhydramine 50 mg (or equivalent) and/or acetaminophen/paracetamol 325 mg to 1000 mg at least 30 minutes before study treatment administrations.

For Grade 2 symptoms (moderate reaction requiring therapy or infusion interruption but responding promptly to symptomatic treatment such as antihistamines, non-steroidal anti-inflammatory drugs, narcotics, corticosteroids, bronchodilators, IV fluids, or prophylactic medications indicated for  $\leq$  24 hours):

• Stop the study treatment infusion, begin an IV infusion of sodium chloride and treat the participant with diphenhydramine 50 mg IV (or equivalent) and/or acetaminophen/paracetamol 325 mg to 1000 mg; remain at bedside and monitor participant

Protocol Amendment No.: 07

until resolution of symptoms. Corticosteroid and/or bronchodilator therapy may also be administered as appropriate. If the infusion is interrupted, then restart the infusion at 50% of the original infusion rate when symptoms resolve; if no further complications ensue after 30 minutes, the rate may be increased to 100% of the original infusion rate. Monitor participant closely. If symptoms recur, then no further BMS-986253 or nivolumab will be administered at that visit.

• For future infusions, the following prophylactic pre-medications are recommended: diphenhydramine 50 mg (or equivalent) and/or acetaminophen/paracetamol 325 mg to 1000 mg should be administered at least 30 minutes before study treatment infusions. If necessary, corticosteroids (up to 25 mg of hydrocortisone or equivalent) may be used.

For Grade 3 or 4 symptoms (severe reaction, Grade 3: prolonged [ie, not rapidly responsive to symptomatic medication and/or brief interruption of infusion]; recurrence of symptoms following initial improvement; hospitalization indicated for other clinical sequelae [eg, renal impairment, pulmonary infiltrates]; Grade 4: Life-threatening; pressor or ventilatory support indicated):

• Immediately discontinue infusion of study treatment. Begin an IV infusion of sodium chloride and treat the participant as follows: recommend bronchodilators, epinephrine 0.2 mg to 1 mg of a 1:1,000 solution for subcutaneous administration or 0.1 mg to 0.25 mg of a 1:10,000 solution injected slowly for IV administration, and/or diphenhydramine 50 mg IV with methylprednisolone 100 mg IV (or equivalent), as needed. Participant should be monitored until the investigator is comfortable that the symptoms will not recur. Study treatment will be permanently discontinued except for a Grade 3 infusion reaction that returns to Grade 1 in less than 6 hours. Investigators should follow their institutional guidelines for the treatment of anaphylaxis. Remain at bedside and monitor participant until recovery of the symptoms.

In case of late-occurring hypersensitivity symptoms (eg, appearance of a localized or generalized pruritus within 1 week after treatment), symptomatic treatment may be given (eg, oral antihistamine or corticosteroids).

# 7.6.7 Management of Cytokine Release Syndrome (CRS)

• Cytokine release plays a role in the pathophysiology of drug-related infusion reactions, which should be managed as per guidelines in Section 7.6.6. Infusions of immune-stimulating agents can also be associated with a cytokine-associated toxicity known as CRS, which has unpredictable onset and could occur many days following treatment. CRS is a clinical syndrome typically associated with infusions of immune-stimulating agents such as chimeric antigen receptor T cell (CAR T-cell) and bispecific antibodies. Cytokine release syndrome is characterized by fever, fatigue, nausea, headache, dyspnea, tachycardia, rigors, hypotension, hypoxia, myalgia/arthralgia, and anorexia. Clinical symptoms and severity of CRS are highly variable, and management can be complicated by concurrent conditions.

• Fever (≥ 38.5°C or ≥ 101.3°F) is a commonly-observed hallmark of CRS, and many features of CRS mimic infection. Hence, infection must be considered in all participants presenting with CRS symptoms, and appropriate cultures should be obtained, and empiric antibiotic therapy initiated per institution standard of care.

- Less common symptoms associated with CRS include cardiac dysfunction, adult respiratory distress syndrome, renal and/or hepatic failure, coagulopathies, disseminated intravascular coagulation, and capillary leak syndrome.
- Neurologic toxicity has been observed concurrently with CRS.
- High baseline levels of other commonly measured inflammatory markers, such as ferritin and C-reactive protein (CRP), were also associated with CRS.

The potential for BMS-986253 in combination with nivolumab or nivolumab plus ipilimumab to cause CRS is not yet defined, and CRS due to immune checkpoint inhibitors is rare. Most guidelines for management of CRS are intended for recipients of CAR T-cell therapy, and widely adopted algorithms to manage CRS specifically due to immune checkpoint blockade have not been established. If CRS is suspected, local guidelines for CRS management with input from BMS Medical Monitor or designee should be followed. General principles for CRS management include use of acetaminophen, steroids, IV fluids, and vasopressors. Interleukin-6 (IL-6), a pleiotropic cytokine with anti-inflammatory and proinflammatory properties, has been identified as a central mediator of toxicity in CRS. In more severe cases, use of tocilizumab, an anti-interleukin-6 receptor monoclonal antibody, may be considered. CRS severity should be documented by CTCAE v4.03 criteria which primarily grades CRS based on clinical judgment as to interventions needed and subsequent response to these treatments. Management of study treatment should be per the table below.

Table 7.6.7-1: Management of Cytokine Release Syndrome (CRS)

Grade (CTCAE v4.03)	Intervention
1	No change to study treatment.
2	Study treatment may resume at next scheduled dose but consider prophylactic supportive therapy, eg, with acetaminophen 500-1000 mg
3	Permanently discontinue study treatment if does not improve to Grade 1 within 6 hours and contact BMS MM or designee.
4	Permanently discontinue BMS-986253 and contact BMS MM or designee.

Abbreviations: BMS, Bristol-Myers Squibb Company; CRS, cytokine release syndrome; CTCAE, Common Terminology Criteria for Adverse Events; MM, medical monitor.

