### 7 TREATMENT

### 7.1 Treatments Administered

Study treatment is defined as any investigational treatment(s), marketed product(s), placebo, or medical device intended to be administered to a study participant according to the study randomization or treatment allocation.

Study treatment includes only the Investigational [Medicinal] Product (IP/IMP) and consist of the following:

- BMS-986253
- Nivolumab
- Ipilimumab
- Placebo for BMS-986253 (socium chloride for injection or dextrose for injection)

An IP, also known as IMP in some regions, is defined as a pharmaceutical form of an active substance or placebo being tested or used as a reference in a clinical study, including products already with a marketing authorization but used or assembled (formulated or packaged) differently than the authorized form, or used for an unauthorized indication, or when used to gain further information about the authorized form.

All drugs used in this study qualify as IPs, as per previous text, and their description and storage information are described in Table 7.1-1.

Other medications used as support or escape medication for preventative, diagnostic, or therapeutic reasons, as components of the standard of care for a given diagnosis, are considered as Non-investigational [Medicinal] Product (Non-IP/Non-IMP).

Protocol Amendment No.: 07

Table 7.1-1: Study Treatments for CA027002

Product Description/ Class and Dosage Form	Potency	IP/ Non-IMP	Blinded or Open Label	Packaging/ Appearance	Storage Conditions (per label)	
BMS-986253 Injection		IP	Open label a	Vial	Refer to the label on container and/or pharmacy manual	
BMS-986253 Injection		IP	Open label a	Vial	Refer to the label on container and/or pharmacy manual	
Nivolumab (BMS-936558) solution for injection		IP	Open label a	Vial	Refer to the label on container and/or pharmacy manual	
Ipilimumab solution for injection		IP	Open label a	Vial	Refer to the label on container and/or pharmacy manual	
Ipilimumab solution for injection		IP	Open label a	Vial	Refer to the label on container and/or pharmacy manual	
Normal saline solution for injection b		IP	Open label	Various (local commercial product)	Refer to the label on container	
Dextrose solution for injection b		IP	Open label	Various (local commercial product)	Refer to the label on container	

Abbreviation: IP, Investigational Product.

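### Table 7.6.7-1 stops all study treatment for unresolved Grade 3 cytokine release syndrome but names only BMS-986253 at Grade 4

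*Combined protocol and SAP*

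**What the plan says.** Section 7.6.7 gives general advice on CRS and then makes its table the operative instruction: "Management of study treatment should be per the table below". Two rows of Table 7.6.7-1 require a permanent stop:

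- Grade 3: "Permanently discontinue study treatment if does not improve to Grade 1 within 6 hours and contact BMS MM or designee".
- Grade 4: "Permanently discontinue BMS-986253 and contact BMS MM or designee".

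Section 7.1 fixes the meaning of the term used in the Grade 3 row: "Study treatment includes only the Investigational [Medicinal] Product (IP/IMP) and consist of the following", followed by BMS-986253, nivolumab, ipilimumab and placebo for BMS-986253. The Grade 1 and Grade 2 rows also speak of study treatment. Only the Grade 4 row names a single drug.

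On cause, Section 7.6.7 says "The potential for BMS-986253 in combination with nivolumab or nivolumab plus ipilimumab to cause CRS is not yet defined". The same sentence goes on to describe CRS from checkpoint inhibitors as rare.

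**The concern.** A stopping rule should not cover fewer drugs as the event becomes more severe, unless a reason is given. Here the list of agents shrinks from the whole regimen to one drug between Grade 3 and Grade 4. The row states no attribution condition and refers to no other section that would supply one.

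What is at stake is participant safety. A site following the table after a Grade 4 event is told what to do with BMS-986253 but not with nivolumab or ipilimumab. After an unresolved Grade 3 event the table permanently bars all of them. After Grade 4 it leaves the checkpoint inhibitors to the general rules, under which they could in principle be resumed.

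The missing reference to placebo adds to this in blinded Part 2. Sections 7.6.3, 7.6.4 and 8.1 write BMS-986253 with placebo in parentheses, but this row does not. A control-arm participant receives only nivolumab and ipilimumab as active drugs, and the row names neither.

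**Working it through.** The plan states no figure to reproduce. The check compares the drugs covered by each rule.

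**Step 1: agents named in the table.** The inputs are the two permanent-stop rows of Table 7.6.7-1, the Section 7.1 definition, the regimens in Table 7.3-1, and the limit on ipilimumab of 4 doses or 12 weeks in Section 5.4.10.

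| Setting | Agents being given | Stopped at unresolved Grade 3 | Named at Grade 4 |
|---|---|---|---|
| Part 2 active arm, first 12 weeks | BMS-986253, nivolumab, ipilimumab | 3 of 3 | 1 of 3 |
| Part 2 active arm, after week 12 | BMS-986253, nivolumab | 2 of 2 | 1 of 2 |
| Part 2 control arm, first 12 weeks, active drugs only | nivolumab, ipilimumab | 2 of 2 | 0 of 2 |

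In each setting the Grade 4 set is smaller than the Grade 3 set and contained in it. In the trigger the order is reversed: Grade 3 allows a 6-hour recovery window and Grade 4 allows none. The Grade 4 row is therefore stricter on when to stop and narrower on what to stop.

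**Step 2: neighbouring rules.**

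- *Infusion reactions, Section 7.6.6, Grade 3 or 4:* "Study treatment will be permanently discontinued except for a Grade 3 infusion reaction that returns to Grade 1 in less than 6 hours". Grade 4 has no exception, and the stop covers all study treatment.
- *Hemophagocytic lymphohistiocytosis, Section 7.6.8.1:* all study treatments stop, whichever agent, if any, is thought responsible.
- *Exceptions to permanent discontinuation, Section 7.6.5:* 12 entries. Five extend to Grade 4 events (electrolytes, neutropenia, lymphopenia or leukopenia, amylase or lipase, endocrinopathy). One concerns CRS: "Grade 3 CRS that returns to Grade 1 in < 6 hours". None covers Grade 4 CRS. The Amendment 05 summary in Appendix 13 lists this CRS entry and the new Section 7.6.7 together. The Grade 3 row matches the entry closely, while the Grade 4 row has no counterpart in the list.

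**Step 3: general rules outside the table.**

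- Section 7.6.3 delays all study drugs for an adverse event that the investigator judges to warrant delay.
- Section 7.6.4 generally requires drug-related events to return to Grade 1 or baseline. Its instruction is then to "resume all study drugs unless the investigator determines that one of the agents must be discontinued due to toxicity attributed to that agent alone".
- Section 8.1 requires a stop when continuing is against the participant's best interest or carries substantial clinical risk. Neither condition depends on the dose-limiting toxicity criteria.
- Section 8.1 assesses each agent separately. If discontinuation criteria are met and attribution cannot be determined, all study drugs stop.
- Sections 7.6.5 and 8.1 also require a stop for events meeting the Section 7.6.1 dose-limiting toxicity criteria. Those criteria are not visible in the public text.

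Steps 1 and 2 show that the row is out of order. Step 3 shows that the protocol as a whole limits the practical consequence.

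**The case against.** The best defence is that the row sets a minimum. BMS-986253 stops in every case, and Section 8.1 decides the rest, including a stop of all drugs when attribution is unclear. The sentence calling checkpoint-inhibitor CRS rare gives some reason to name the investigational agent. The row requires Medical Monitor contact, and Section 7.6.7 also points sites to local CRS guidelines with Medical Monitor input. CRS and infusion reactions are treated as separate syndromes, so their rules need not be identical.

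Most of this stands, and it sets the size of the point. It does not remove the mismatch. The Grade 3 row requires the same Medical Monitor contact and still states the full stop. Rarity does not settle which drug caused a particular Grade 4 event. The row does not refer to Section 8.1, so the minimum-stop reading has to be assembled from elsewhere.

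A reader might infer more than the documents support:

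- *That the protocol authorises nivolumab and ipilimumab to continue after Grade 4 CRS.* It does not. The row is silent on them, and the general rules in Step 3 still apply.
- *That the row contradicts the dose-limiting toxicity rules.* This cannot be shown, because the Section 7.6.1 criteria are not visible. If Grade 4 CRS meets them, Section 7.6.5 already stops all study drugs unless the toxicity is attributed to one agent alone.
- *That a control-arm participant would have nothing stopped.* Part 2 is double-blind, so a blinded site would be expected to stop the blinded infusion. The valid point is that the row names neither of that participant's active drugs.

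**Conclusion.** Wrong as written, minor. The Grade 4 row covers fewer agents than the row below it in severity, omits placebo, and does not fit the comparable rules in Sections 7.6.5, 7.6.6 and 7.6.8.1. This rests on the current Amendment 07 text and on reading study treatment as Section 7.1 defines it.

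The practical risk is low. The Document History entry for Amendment 05 records no CRS events when the guidance was added. Ipilimumab exposure is short, and Amendment 07 plans the Part 2 final analysis on participants already enrolled. The rule therefore now matters mainly for nivolumab in participants still on treatment. Treatment can last 3 years, or up to 5 with clinical benefit (Section 7.11), so the rule is still live. No effect on the comparison between arms is claimed.

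**What to change.** In the Grade 4 row of Table 7.6.7-1, replace the single drug name with the term study treatment, keeping the stop unconditional and the Medical Monitor contact as it is. Because Section 7.1 includes placebo in that term, this also closes the placebo gap.

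If the sponsor wants to allow a single-agent stop where toxicity is attributed to one drug alone, add that condition to both the Grade 3 and the Grade 4 rows, citing Sections 7.6.5 and 8.1. Adding it only at Grade 4 would leave the more severe grade with the more lenient rule.

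The change should be made in the next approved amendment. Appendix 2 requires documented approval of an amendment before a protocol change, except to remove an immediate hazard. The cost is the wording of one table row, or two with the attribution condition. Data collection, sample size and analysis are unaffected.
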